#### 10.4.4 Safety Analyses

Safety analysis will focus on presence and absence of DLT, and incidence of lesser toxicities to each agent or both.

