A phase 3 pivotal multicenter single-arm trial (NCT01829711) was designed for relapsed/refractory HCL patients with ≥2 prior systemic therapies including ≥1 prior purine analog. Patients received moxetumomab pasudotox-tdfk 40 mcg/kg intravenously on days 1, 3, and 5 of each 28-day cycle for 6 cycles, or until MRD-negative CR, disease progression, initiation of alternate therapy, or unacceptable toxicity. Disease response and immunohistochemistry MRD status were determined by blinded independent central review. The primary endpoint was durable CR, which required achieving CR and maintaining hematologic remission (HR) for >180 days). HR was defined as hemoglobin >11.0 g/dL, absolute neutrophil count >1.5/nL, and platelet count ≥100/nL without transfusions or growth factors within the preceding 4 weeks of assessments. Eighty patients (63 males, 17 females; median age 60 years (range 34-84) were enrolled. The median number of previous systemic therapies was 3 (2–11); 48.8% of patients were purine analog refractory and 37.5% were unfit for purine analog retreatment. The median number of treatment cycles administered was 6 (1-7). As of May 24, 2017, the durable CR rate was 30.0%, 24/80 patients; 95% confidence interval (CI): 20.3, 41.3). CR rate was 41.3% (33/80 patients; 95% CI: 30.4, 52.8), and ORR was 75% (95% CI: 64.1, 84.0). Among 33 patients who achieved a CR, 27 (81.8%) also achieved MRD negativity. Median time to OR was 5.7 months (95% CI: 5.7, 5.9). Sixty-four patients (80%) achieved hematologic remission. The median duration of hematologic remission from CR, median duration of response, and PFS were not reached.

Of 64 patients treated on the phase 1 (NCT01087333) and 3 (NCT01829711) trials at NIH with 40-50 mcg/kg dose levels of moxetumomab pasudotox-tdfk and evaluated for MRD by bone marrow aspirate flow cytometry, the 30 (47%) of 64 achieved MRD-free CR.

The most frequently reported adverse events (AEs) occurring in >40% of subjects overall were hypoalbuminemia (71.4%), increased ALT (67.3%); increased AST (63.3%), lymphopenia (59.2%), myalgia (57.1%); decreased white blood cell count (51.0%); pyrexia (49.0%); peripheral edema (44.9%); and hypertriglyceridemia (40.8%).

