A total of 48 phase I subjects (98%) had AEs that were assessed by the investigator as related (possibly, probably, or definitely) to investigational product. The most frequent treatment-related AEs occurring in > 20% of subjects were hypoalbuminemia (69.4%), increased ALT (63.3%), increased AST (61.2%), peripheral edema (42.9%), pyrexia (42.9%), myalgia (40.8%), headache (36.7%), nausea (32.7%), fatigue (28.6%), edema (24.5%), hypotension (24.5%), and chills (22.4%). Treatment-related grade 3/4 AEs were reported in 30.0% of patients. Three deaths were reported (due to pneumonia, sepsis, and sepsis syndrome); none were considered treatment-related by the investigators. Treatment-related AEs that most frequently led to permanent discontinuation were hemolytic uremic syndrome (HUS), capillary leak syndrome (CLS), and blood creatinine increased, reported in 4 (5.0%), 2 (2.5%), and 2 (2.5%) patients, respectively. Seven patients (8.8%) had CLS (grade 2: n=5; grade 4: n=2), 7 patients (8.8%) had HUS (grade 2: n=2; grade 3: n=3; grade 4: n=2), and 4 patients (5.0%) had both CLS and HUS. In general, CLS and HUS events were manageable and reversible with appropriate supportive care, monitoring, and, in severe events, treatment discontinuation. Grade 3-4 AEs, regardless of attribution, occurring in at least 2.5% of patients included lymphopenia (20%), hypophosphatemia or anemia (10%), leukopenia

Version Date: 04/16/2025

(8.8%), hypertension, (7.5%), thrombocytopenia or neutropenia (6.3%), HUS, febrile neutropenia, or neutropenia (5%), and nausea, hypokalemia, hyponatremia, CLS, upper respiratory infection, hypoxia, lung infection, acute kidney injury, or erysipelas (2.5%). A number of eye changes have been reported in studies with moxetumomab pasudotox-tdfk; serious events including inflammation of the nerve for sight and retinal detachment have occurred in the acute lymphoblastic leukemia [14].

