## 3 STUDY IMPLEMENTATION

## 3.1 STUDY DESIGN

This is a Phase 1 trial, two-arm, non-randomized trial involving the administration of moxetumomab pasudotox-tdfk 30-40 mcg/kg iv and rituximab/Ruxience 375 mg/m² iv, 50-400 mg/hr. The purpose of the rituximab/Ruxience is to decrease the HCL tumor burden, allowing the

Version Date: 04/16/2025

63 kDa immunotoxin to reach all the malignant cells, thereby facilitating tumor eradication, and prevention of neutralization of the immunotoxin by the immune system, through the action of rituximab/Ruxience on normal B-cells. To allow sufficient time for the rituximab/Ruxience to act prior to moxetumomab pasudotox-tdfk, in the first cycle, rituximab/Ruxience will be given on day -2 followed by moxetumomab pasudotox-tdfk on days 1, 3 and 5. Thus on cycle 1 only, moxetumomab pasudotox-tdfk will begin on the 3rd day after rituximab/Ruxience. On subsequent cycles, spaced ~ 4 weeks (as few as 25 days) apart, rituximab/Ruxience will begin on day 1 and moxetumomab pasudotox-tdfk on days 1, 3 and 5. Participants will receive up to 4 cycles past documentation of CR without MRD, up to a maximum of 8 cycles which means, no participant in this trial will receive more than 8 cycles.

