# 8.1.5 Relationship to Study Product

All AEs will have their relationship to study product assessed using the terms: related or not related.

- Related There is a reasonable possibility that the study product caused the adverse event. Reasonable possibility means that there is evidence to suggest a causal relationship between the study product and the adverse event.
- Not Related There is not a reasonable possibility that the administration of the study product caused the event.

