#### 8.2 ASSESSMENT OF SAFETY EVENTS

AE information collected (see Section **8.4.4**) will include event description, date of onset, assessment of severity and relationship to study product and alternate etiology (if not related to study product), date of resolution (return to baseline or stabilization) of the event, seriousness and outcome. The assessment of severity and relationship to the study product will be done only by those with the training and authority to make a diagnosis and listed on the Form FDA 1572 as the site principal investigator or sub-investigator. AEs occurring during the collection and reporting period will be documented appropriately regardless of relationship. AEs will be followed through resolution.

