## 8.4.4 Requirements of adverse events (AEs) reporting

The following variables will be collected for each AE:

AE (verbatim)

- The date and time when the AE started and stopped
- Select the appropriate if needed: maximum intensity or intensity or changes in intensity
- Changes in NCI CTCAE grade and the maximum CTC grade attained
- Whether the AE is serious or not
- Investigator causality rating against the Investigational Product (yes or no) comparator/combination drug (yes/no)
- Action taken with regard to investigational product/comparator/combination agent
- Outcome

In addition, the following variables will be collected for SAEs:

- Date AE met criteria for serious AE
- Date Investigator became aware of serious AE

- AE is serious due to
- Date of hospitalization
- Date of discharge
- Probable cause of death
- Date of death
- Autopsy performed
- Description of AE
- Causality assessment in relation to Study procedure(s)
- Causality assessment in relation to other medication
- Causality assessment in relation to Additional Study Drug

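### Section 10.4.4 plans toxicities below DLT only by attribution to a study drug, so events judged related to neither drug have no stated place in the safety analysis

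*Combined protocol and SAP*

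**What the plan says.** One sentence plans the analysis of toxicities below DLT (10.4.4): "Safety analysis will focus on presence and absence of DLT, and incidence of lesser toxicities to each agent or both". DLT itself is restricted to treatment-related events of grade 3 or higher, with listed exceptions (3.1.2).

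Attribution is made by the investigator. Section 8.1.5 states: "All AEs will have their relationship to study product assessed using the terms: related or not related". Section 8.4.4 adds a rating for each drug: "Investigator causality rating against the Investigational Product (yes or no) comparator/combination drug (yes/no". An event can therefore be related to one drug, to the other, to both or to neither.

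Collection is wider than the planned analysis. Section 8.2 says: "AEs occurring during the collection and reporting period will be documented appropriately regardless of relationship". Every participant is evaluable for toxicity from first treatment (10.3.1). Section 6.1, however, records a laboratory abnormality as an adverse event only if it meets one of several conditions, such as symptoms, need for treatment, discontinuation or significant clinical impact.

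On dosing, Section 3.1 says of cycle 1: "rituximab/Ruxience will be given on day -2 followed by moxetumomab pasudotox-tdfk on days 1, 3 and 5". For later cycles: "rituximab/Ruxience will begin on day 1 and moxetumomab pasudotox-tdfk on days 1, 3 and 5".

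The general statement at 10.4.1–10.4.2 says that safety data, like the MRD-free CR rate, will be evaluated in comparison with prior trials.

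**The concern.** The primary objective is the safety of the combination (1.1.1). Both arms receive it, so the trial has no concurrent group to show how often an event would occur without it. An investigator who knows the treatment decides whether an event belongs to a drug, to the leukemia or to something else. Under the wording of 10.4.4, an event assigned to neither drug drops out of the stated analysis.

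Two things are at stake. The reported toxicity of the combination may be too low, by an amount that a reader could not judge from attributed tables alone. The comparison with prior trials may also be distorted: 1.2.1 gives overall rates for phase 1 and grade 3-4 rates regardless of attribution. If attributed rates from this trial were set beside those, the combination could look safer than monotherapy through the counting rule alone.

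**Working it through.** **The plan's own safety figure.** Section 10.2 gives 45.0% as the upper one-sided 90% confidence bound on 2 DLTs in 10. The exact (Clopper-Pearson) bound is the 0.90 quantile of Beta(3, 8) = 0.4496, so the figure reproduces. The point here does not depend on it.

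**What attribution removed in phase 1.** Section 1.2.1 gives overall and treatment-related percentages. The denominator is inferred as 49: 28 + 21 subjects in the phase 1 description, 48/49 = 98%, and each percentage below is a whole number out of 49. The treatment-related list stops at 20%, and 0.20 × 49 = 9.8. If that list is complete, an event missing from it had at most 9 attributed subjects.

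| Event | Overall | Related | Not attributed |
|---|---|---|---|
| Myalgia | 57.1% = 28 | 40.8% = 20 | 8 of 28 (29%) |
| Pyrexia | 49.0% = 24 | 42.9% = 21 | 3 of 24 (12.5%) |
| Peripheral edema | 44.9% = 22 | 42.9% = 21 | 1 of 22 (5%) |
| Hypoalbuminemia | 71.4% = 35 | 69.4% = 34 | 1 of 35 (3%) |
| Increased ALT | 67.3% = 33 | 63.3% = 31 | 2 of 33 (6%) |
| Increased AST | 63.3% = 31 | 61.2% = 30 | 1 of 31 (3%) |
| Lymphopenia | 59.2% = 29 | not listed, ≤ 9 | ≥ 20 of 29 (69%) |
| Decreased white cells | 51.0% = 25 | not listed, ≤ 9 | ≥ 16 of 25 (64%) |
| Hypertriglyceridemia | 40.8% = 20 | not listed, ≤ 9 | ≥ 11 of 20 (55%) |

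The effect is uneven: small for some events, large for others. The last three rows are laboratory findings and weigh least here, because the recording rule in 6.1 may keep many such values out of this trial's adverse event data altogether.

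**Does confusion between the two drugs lower the combined count?** Take 10 drug-caused events (an assumed number) and split them as moxetumomab only / antibody only / both:

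- 5/2/3: total 10; any moxetumomab 5 + 3 = 8; any antibody 2 + 3 = 5
- 2/1/7: total 10; any moxetumomab 9; any antibody 8
- 0/0/10: total 10; any moxetumomab 10; any antibody 10

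The per-agent figures move and the total does not. The total falls only when a drug-caused event is rated unrelated to both drugs. With assumed shares of 0%, 10%, 20% and 30%, the count is 10, 9, 8 and 7. The documents give no such share for this trial.

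**How much the dosing overlaps.** Over a full 8 cycles there are 3 × 8 = 24 moxetumomab doses. Day 1 of cycles 2-8 is shared with the antibody, so 7 of the 24 coincide and 17 do not. Seen from the antibody, 7 of its 8 doses fall on a moxetumomab day. Section 1.2.1 also says that rituximab keeps normal B-cells undetectable for at least 6 months after the last dose, so days 3 and 5 do not cleanly separate effects that are not infusion reactions. Only the interval from day -2 of cycle 1 to the first moxetumomab dose is antibody alone.

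**The case against.** A reader might infer that, because both drugs are infused on the same day in cycles 2-8, the combination's toxicity will be understated. The documents do not support this. Section 10.4.4 has a class for events due to both agents, and 8.4.4 rates each drug separately, so an event that cannot be assigned to one drug can be rated yes for both and still be counted. The overlap is also one day per cycle.

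Four further objections carry weight.

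- The gap between overall and related rates is not in itself bias, since some excluded events were truly unrelated. This stands: understatement is possible, not shown.
- The phase 1 gap cannot be carried over directly. Relatedness there covered possible, probable and definite; here it is a binary judgement of reasonable possibility (8.1.5). This stands.
- Section 1.2.1 also gives treatment-related rates, so attributed results have an attributed comparator. This is true, but it leaves the all-cause rates there without a counterpart.
- Section 10.4.4 says the analysis will focus on these items, which does not forbid others, and the general statement on safety data has no attribution limit. That makes this a missing commitment rather than a prohibition. Still, no sentence promises a table regardless of attribution.

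**Conclusion.** The point holds in a limited form. The stated safety analysis is attribution-based throughout, and events judged related to neither drug have no place in it. Without a concurrent control this can understate the combination's toxicity, and it leaves the planned comparison with prior trials without an all-cause table on this trial's side.

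The best indication of size is the phase 1 monotherapy experience: 8 of 28 subjects with myalgia and 3 of 24 with pyrexia were not attributed, an unknown part of them drug-caused. This rests on the inferred denominator of 49 and on both lists describing the same phase 1 subjects. It shows what attribution can remove and does not estimate what it will remove here.

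Same-day dosing is a reason to treat the per-agent split with caution, not a cause of undercounting. The criterion of at most 2 DLTs in 10, the sample size and the power are unaffected.

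**What to change.** Reword 10.4.4 so that:

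- the main safety table is the incidence of all recorded adverse events by maximum grade, regardless of attribution, from the first dose of either drug;
- events between the cycle 1 day -2 antibody dose and the first moxetumomab dose are shown separately;
- attribution to each agent, or to both, is kept as a secondary table;
- prior-trial comparisons set all-cause against all-cause rates and attributed against attributed rates, noting the different relatedness scales;
- a note says that the recording rule in 6.1 limits which laboratory abnormalities count as adverse events, so laboratory adverse event rates may not be comparable with prior trials.

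Two details of collection should be settled with it. Section 6.1 starts recording at the first study intervention but calls this Study Day 1, whereas the antibody is given on day -2 and 8.4.3.2 collects from consent; the antibody-only table needs the earlier start. Section 6.1 also requires only serious, related events after 30 days, so the all-cause table should end there.

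The cost is a short rewording and extra tables from adverse events already to be recorded. Reported rates will be somewhat higher.

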# 10.4.5 Sub-Group Analyses

Not Applicable.

## 10.4.6 Exploratory Analyses

Results of exploratory analyses will be descriptive.

#### 11 COLLABORATIVE AGREEMENTS

#### **11.1 CRADA**

Conduct of this study and supply of moxetumomab pasudotox-tdfk and rituximab/Ruxience will be addressed by amendment (#13) to existing NCI CRADA (#1975) with AZ.

#### 12 HUMAN SUBJECTS PROTECTIONS

#### 12.1 RATIONALE FOR SUBJECT SELECTION

Participants eligible will be relapsed. Defining the safety of moxetumomab pasudotox-tdfk in participants with relapsed HCL will be needed before considering extending this regimen to participants after only 1 or no prior therapy.

#### 12.2 Participation of Children

HCL has not been reported in individuals < 18 therefore children will not participate in this study.

#### 12.3 PARTICIPATION OF SUBJECTS UNABLE TO GIVE CONSENT

Adults unable to give consent are excluded from enrolling in the protocol. However, it is possible that subjects enrolled in the protocol may permanently lose the capacity to consent for themselves during the course of this study. In the event this occurs, the subjects will remain in the study because there is a prospect of direct benefit from research participation (Section 12.5.1). ,All subjects ≥ age 18 will be offered the opportunity to fill in their wishes for research and care, and assign a substitute decision maker on the "NIH Advance Directive for Health Care and Medical Research Participation" form so that another person can make decisions about their medical care in the event that they become incapacitated or cognitively impaired during the course of the study.

Note: The PI or AI will contact the NIH Ability to Consent Assessment Team (ACAT) for evaluation to assess ongoing capacity of the subjects and to identify an LAR, as needed.

Please see Section 12.5.1 for consent procedure.

#### 12.4 EVALUATION OF BENEFITS AND RISKS/DISCOMFORTS

Participants will receive evaluation of their disease at the National Cancer Institute's Clinical Center. This protocol may or may not benefit an individual, but the results may help the

Version Date: 04/16/2025

investigators learn more about the disease and develop new treatments for participants with this disease.

Potential adverse reactions attributable to the administration of the drugs utilized in this trial are discussed in Sections 14.1.2 and 14.2.2. All care will be taken to minimize side effects, but they can be unpredictable in nature and severity. Participants will be examined and evaluated prior to enrollment. All evaluations to monitor the treatment of participants will be recorded in the participant chart. If participants suffer any physical injury as a result of the participation in this study, immediate medical treatment is available at the Clinical Center, National Cancer Institute, Bethesda, Maryland.

Although no compensation is available, any injury will be evaluated and treated in keeping with the benefits or care to which participants are entitled under applicable regulations. In all publications and presentations resulting from this trial, participants' anonymity will be protected to the maximum extent possible. Authorized personnel from the National Cancer Institute (NCI) and Food and Drug Administration (FDA) or other regulatory authorities may have access to research files in order to verify that participants' rights have been safeguarded. In addition, participant names will be given to the Central Registration to register and verify participants' eligibility.

## 12.4.1 Potential Risks Associated with Administration of Moxetumomab pasudotox-tdfk

The primary risks of participation in this study include the possible occurrence of any of a range of side effects from moxetumomab pasudotox-tdfk are described in Sections 1.2.1, 14.1.2 and in the consent document. Frequent monitoring for adverse effects and exclusion of subjects at risk for these adverse effects will help to minimize the risks associated with administration. Moxetumomab pasudotox-tdfk is administered intravenously. Possible risks associated with IV administration of moxetumomab pasudotox-tdfk are infection, redness, swelling, pain, and induration at the administration site.

#### 12.4.2 Potential Risks Associated with Administration of Rituxan

Refer to Section 14.2.2 for details.

#### 12.4.3 Potential Risks Associated with Administration of Ruxience

Refer to Section 14.3 for details.

## 12.4.4 Identified Risks to Study Procedures

#### 12.4.4.1 Blood Sampling

Side effects of blood draws include pain and bruising, lightheadedness, and rarely, fainting. Up to 123 mL of research blood may be collected at any visit but no more than 315 ml in an 8 week period. Refer to study calendar (Section 3.4) for frequency of blood draws.

## 12.4.4.2 Urine Collection

There is no physical risk involved with urine collection.

## 12.4.4.3 Bone marrow aspirate and/or biopsy

Bone marrow biopsy is minimally invasive and is typically a very safe procedure. Usually, hipbone is numbed with anesthesia. Using a needle, the solid and liquid portion of bone marrow is taken out. This procedure causes some pain. Very rarely, infection or bleeding may occur at the needle site.

## 12.4.4.4 Electrocardiogram

Some skin irritation can occur where the ECG/EKG electrodes are placed. The test is completely painless and generally takes less than a minute to perform.

#### 12.4.4.5 Stress test

A stress test is generally safe, and complications are rare. Risks include hypotension, arrhythmias, or myocardial infarction.

## 12.4.4.6 Pulmonary function tests (PFTs)

PFTs are usually safe for most people. Risks include dizziness, asthma attack, or collapsed lung.

### 12.4.4.7 Abdominal ultrasounds and echocardiogram

There is no physical risk involved with abdominal ultrasounds or echo.

## 12.4.4.8 Imaging

In addition to the radiation risks discussed below, CT scans may include the risks of an allergic reaction to the contrast. Participants might experience hives, itching, headache, difficulty breathing, increased heartrate and swelling.

The risks of MR imaging are relatively small.

The US Food and Drug Administration has issued warnings that administration of gadolinium (updated September 9, 2010), the MRI contrast imaging agent used in this protocol, has been associated with development of a disease called nephrogenic systemic fibrosis (NSF). The syndrome is rare (approximately 600 cases reported worldwide as of September 2010, out of several million administrations of gadolinium), but disabling and in some cases, fatal. All cases to date have occurred in participants with severe renal disease, including participants on dialysis. NSF has been nearly eradicated secondary to careful screening of renal function and avoiding use of gadolinium in participants with eGFR <30 ml/min/1.73 BSA. Even in participants with end stage renal disease, there have been only rare occurrences of NSF because of precautions taken to use more stable contrast agents at lower doses. This protocol excludes participants with severe renal insufficiency (eGFR <30 ml/min/1.73 BSA). The FDA has issued warnings in 2017 and 2018 that some gadolinium may be retained in the brain, bone and skin although health risks of accumulation have not been reported to date. In accordance with the FDA Drug Safety Communication of 05/16/2018, the Medication Guide for gadobutrol (or other macrocyclic gadolinium contrast agent if applicable) will be made available to all participants with scans that will involve gadolinium-based contrast agent administration.

